5.3 Statistical Methods

- **Baseline Data.** Sociodemographics and baseline clinical characteristics will be summarized with descriptive statistics.
- **Efficacy Analysis.** Study hypotheses will be tested using intent-to-treat or modified intent-to-treat methods, as appropriate. For patient-only outcomes, differential treatment effects will be tested with multilevel mixed-effects models with fixed effects and two-way interactions for Time and Treatment and a random effect for Patient. For outcomes assessed in both patients and partners, differential treatment effects will be tested with multilevel mixed-effects models with fixed effects and two- and

three-way interactions for Time, Treatment, and Participant Status (i.e., Patient or Partners) and random effects for Participant and Couple. Linear, logistic, and Poisson distribution functions will be used to model outcome variables. Treatment satisfaction, assessed at post-treatment only, will be compared between patients in UNITE and CBT-E with linear regression.

- **Safety Analysis.** Adverse events will be summarized as a numerator (total affected) and denominator (number at risk) for patients and partners in each treatment arm using the ClinicalTrials.gov categories of all-cause mortality, serious adverse events, and other (not including serious) adverse events.

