MSI-R (AFC, PSC)	Marital Satisfaction Inventory-Revised (Affective Communication, Problem-Solving Communication Subscales)
EDQOL	Eating Disorders Quality of Life
CSQ	Client Satisfaction Questionnaire

PROTOCOL SYNOPSIS

Study Title	Targeting Relationship Domains in Community-Based Treatment of Binge-Eating Disorder
Funder	NIMH
Study Rationale	Clinicians' options for BED treatment are inadequate. Treatments for BED have demonstrated efficacy in controlled settings with specialist therapists and expert supervision, but much less is known about the effectiveness of BED interventions and whether the transition of evidence-based treatments to the community results in poorer outcomes. UNITE activates a key resource by incorporating an important part of the patient's social environment (the partner) into treatment. The investigators hypothesize that UNITE will show preliminary evidence of being superior to CBT-E in achieving binge abstinence via engaging ED-related relationship targets, including improved (a) communication around the disorder, (b) disorder-specific interpersonal problem-solving/ behavioral change skills, and (c) partner-assisted emotion regulation. The investigators will assess targeted relationship domains with observational and speech prosody measures during clinic interactions and self-reports reflecting experiences outside of the clinic. Because the couple is learning how to work together to address BED, the investigators hypothesize that maintenance of gains will show evidence consistent with superiority in UNITE.
Study Objective(s)	Primary 
• To compare the effectiveness of UNITE versus CBT-E in achieving abstinence from binge-eating. Secondary 
• To compare the effectiveness of UNITE versus individual CBT-E in decreasing ED-related psychopathology, depression, and anxiety.• To compare target relationship domains in patients and partners.• To compare treatment satisfaction and ED-related quality of life in UNITE versus CBT-E

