Study Design	38 couples will be enrolled over 18 months (to aim for 34 couples who complete the intervention). Each couple will be randomly assigned to UNITE or CBT-E and will undergo 16 weeks of study treatment. Preliminary efficacy (e.g., changes in binge-eating frequency, depression, anxiety, and relationship functioning) of UNITE will be assessed in comparison to the control group (CBT-E). Treatment gains will be assessed including observational and self-report measures.
Subject Population key criteria for Inclusion and Exclusion:	Inclusion Criteria 
1. Subjects age 18 – 992. Current DSM-5 criteria for BED (one partner per couple)3. English speaking and able to read4. In a committed relationship for at least 6 months (regardless of sexual orientation)

5. Live with partner (or interact with each other daily)
6. Partner willingness to participate in treatment
7. Able to travel to Chapel Hill, NC weekly for treatment (N.B. Changed in 3/20 to "in North Carolina" due to pandemic)

Exclusion Criteria

1. Alcohol or drug dependence in the past year
2. Current anorexia nervosa; current bulimia nervosa
3. Current significant suicidal ideation with active suicidal intent
4. Severe depression that would seriously interfere with functional capacity
5. Developmental disability that would impair the ability to benefit from the intervention
6. Any psychosis, schizophrenia, or bipolar I disorder, unless stably remitted on maintenance therapy for at least 1 year
7. Moderate to high reported levels of physical violence from either partner
8. Unwillingness to forgo non-protocol concurrent couple therapy
9. Previously participated in the UNITE pilot trial

Number of Subjects	76 (38 couples)
Study Duration	Each subject's participation will last approximately 20-30 hours over 10 months. The entire study is expected to last two years.

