Statistical and Analytic Plan	Intent-to-treat or modified intent-to-treat, if appropriate, will comprise the primary approach. Differential treatment effects will be analyzed with multilevel mixed-effects models with fixed effects and interactions for Time, Treatment, and (where appropriate) Participant Status (i.e., patients/partners), and with random effects to address clustering.
Data and Safety Monitoring Plan	The DSMG will be responsible for data quality management and ongoing assessment of participant safety.

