2 STUDY OBJECTIVE

2.1 Primary Objective: The purpose of this study is to test the feasibility, acceptability, and preliminary effectiveness of a novel couple-based intervention for BED (UNITE) relative to an established evidence-based individual treatment (CBT-E) in a community clinic setting.

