3.2 Study Duration, Enrollment and Number of Subjects

38 couples will be enrolled over 18 months (to aim for 34 couples who complete the intervention). Each couple will be randomized to either UNITE or CBT-E and will undergo 16 weeks of treatment, followed by follow-up assessments at the end of treatment and 3- and 6-months after the end of treatment.

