3.3 Study Population: see Protocol Synopsis “Subject Population”

4 STUDY PROCEDURES

4.1 Screening/Baseline Visit procedures

Pre-Treatment

1. Patient and partner come in for pre-treatment visit, which includes the following:

- Consent with both patient and partner
- Videotaped couple interaction
- Interviews
- Self-report Questionnaires

2. Eligibility is determined

3. Couple is randomized to UNITE or CBT-E condition

4. Therapist is assigned and notified

- Baseline (Pre-Treatment)

- Consent
- Background information
 - *Background Information* (1 min). This questionnaire asks questions about age, sex, race/ethnicity, socioeconomic status, and relationship history.
- Couple Interaction
 - Couple is recorded having two 10-minute conversations:
 - For the first conversation (“sharing thoughts and feelings”) the couple is given the prompt: Please select an issue in your relationship related to [patient’s] eating disorder, sharing your thoughts and feelings with each other about this issue. Don’t attempt to resolve it, just let each other know what you think and feel. Try to select something that you view as being of a moderate level of concern or intensity.
 - For the second conversation (“problem-solving”), the couple is given the prompt: I will again ask you to select an issue in your relationship related to [patient’s]

eating disorder, but this time you will discuss ways you could resolve or improve this issue. Try to select something that you view as being of a moderate level of concern or intensity. That is, don't select something trivial, but also don't select the most difficult concern that you have."

- For each conversation, the interviewer may assist the couple in identifying a topic for conversation. Then, the interviewer leaves the room during the 10-minute recorded conversation.
- Vitals (Patient, Partner)
 - Self-reported height, weight, BMI
- Questionnaire (Patient, Partner)
 - ED100K, EDE-Q, BES, BE frequency, BDI-II, BAI, DERS, DERS-Partner, DAS, CPQ-SF, R-BISF, CTS-2, MSI-R, EDQOL
- Interview (Patient, Partner)
 - Videotaped couple interaction
 - MINI, YBOCS-BE

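### Section 5.3 names no tested term, Time coding or baseline role for primary abstinence; if the Time-by-Treatment interaction is the test, it has little power for a moderate, steady UNITE benefit

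*Combined protocol and SAP*

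**What the plan says.** The first primary objective in the Protocol Synopsis is "To compare the effectiveness of UNITE versus CBT-E in achieving abstinence from binge-eating". Section 5.1 defines the primary outcome as 28-day abstinence on the EDE-Q and attaches no visit to it. Section 5.3 gives the model: "For patient-only outcomes, differential treatment effects will be tested with multilevel mixed-effects models with fixed effects and two-way interactions for Time and Treatment", plus a random effect for Patient. Linear, logistic and Poisson forms are listed, so a binary outcome would take the logistic form.

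The synopsis analysis entry describes the same model family: "multilevel mixed-effects models with fixed effects and interactions for Time, Treatment, and (where appropriate) Participant Status". It adds no tested term, no Time coding and no role for baseline.

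The EDE-Q is collected before treatment (section 4.1 lists "ED100K, EDE-Q, BES, BE frequency, BDI-II, BAI") and again at mid-treatment, post-treatment, 3 months and 6 months. Section 12 says the main paper will report the last three of these, without ranking them. Section 5.4 gives no power for the primary test.

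The synopsis rationale adds a second hypothesis, that "maintenance of gains will show evidence consistent with superiority in UNITE".

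**The concern.** A Time-by-Treatment model can yield several tests of a treatment effect, and they answer different questions. A contrast between arms at one visit, or averaged over visits, asks whether more UNITE patients are abstinent. The interaction asks whether the difference between arms changes over time.

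For a continuous outcome with baseline as a Time level, the distinction matters less, because the interaction then compares change from baseline and can detect a benefit that is constant afterwards. Abstinence is different. Patients must meet "Current DSM-5 criteria for BED (one partner per couple", so baseline abstinence is probably near 0% in both arms. That is an inference; no rate is given. A baseline cell of that kind says almost nothing about the log-odds ratio, so a categorical baseline level gives the interaction little to compare with.

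If the interaction were taken as the primary test, a real and steady benefit of moderate size would usually be reported as no differential effect.

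**Working it through.** **Inputs from the document.** Section 3.2: "38 couples will be enrolled over 18 months (to aim for 34 couples who complete the intervention", an implied loss of 1 − 34/38 = 10.5%. Section 7: 1:1 allocation, so about 38/2 = 19 patients per arm. Section 5.4 gives no power figure to reproduce.

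**Assumptions.** Two-sided alpha of 0.05; all abstinence rates; patient random-intercept SD 1.5 or 2.5; loss of 2 per arm, at random, from post-treatment on. Section 3.2 does not give the split or timing of loss, and not completing treatment is not the same as missing assessments.

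**Step 1: what the interaction sees.** For 60% v 30% at every post-baseline visit, the log-odds ratio is ln(0.6/0.4) − ln(0.3/0.7) = 0.405 + 0.847 = 1.253 each time. Among post-baseline visits the interaction is 1.253 − 1.253 = 0.

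**Step 2: what baseline adds.** With 0 of 19 abstinent in both arms, the baseline log-odds ratio cannot be estimated. With 5%, 0.05 × 19 = 0.95 patients per arm are expected to be abstinent. Its standard error is √[2(1/0.95 + 1/18.05)] = 1.49, larger than the 1.253 to be detected. At one later visit with 17 per arm it is √[1/(17×0.24) + 1/(17×0.21)] = 0.72. As a rough guide that ignores within-patient correlation:

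- change from baseline: z = 1.253/√(1.49² + 0.72²) = 0.76, power about 12%
- arm contrast at that visit: z = 1.253/0.72 = 1.73, power about 41%

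The standard two-proportion formula with 17 per arm also gives 42% for that visit.

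**Step 3: simulation.** Random-intercept logistic models were fitted by maximum likelihood (15-point Gauss-Hermite) with likelihood-ratio tests and 500 replicates per cell (Monte Carlo error up to about 4 points). Linear Time was 0, 2, 4, 7 and 10 months. The table gives the percentage of trials that reject, as ranges over SD and rates. The 3 df column refers the same statistic to 3 rather than 4 degrees of freedom.

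| Gap between arms | Categorical interaction, baseline kept: 4 df / 3 df | Linear interaction, baseline kept | Baseline dropped: categorical / linear | Average of post, 3, 6 months | Post-treatment alone |
|---|---|---|---|---|---|
| Constant (60v30, 50v25), 0% baseline | 3–4 / 7–11 | 6–10 | 7–9 / 6–7 | 48–73 | 35–44 |
| Same, 5% baseline | 12–19 / 19–27 | 5–14 | 6–8 / 6–7 | 53–71 | 32–45 |
| Late-opening | 6–10 / 11–19 | 16–20 | 11–19 / 10–15 | 66–70 | 43–48 |
| Widening | 13–31 / 20–41 | 34–49 | 20–40 / 24–48 | 49–73 | 16–24 |
| Fading | 10–18 / 19–24 | 3–7 | 19–24 / 18–25 | 27–32 | 44–47 |
| None (40v40) | 3–4 / 6 | 2 | 6 / 5 | 8 | 7–8 |

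Patterns at mid, post, 3 and 6 months (0% baseline):

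- late-opening: 30v20, then 60v30
- widening: 30v30, 60v45, 60v35, 60v25; or 35v20, 55v35, 60v30, 65v25
- fading: 40v20, 60v30, 50v35, 45v40

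The last row shows that the contrasts are slightly liberal, so their power is slightly flattered, while the 4 df and linear tests with baseline kept are conservative. With 5 per arm lost and a constant 60v30, the averaged contrast has 55–63% and the interactions 4–9%.

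**Step 4: other rates.** With complete follow-up and 1,000 replicates, 70v40 gives 16–20% for the linear interaction with baseline kept, over SD 0.7–2.5 and 0% or 5% baseline. For 80v40 that test reaches 43–48% across runs with and without loss. The categorical interaction stays at 3–9% (0% baseline), and the averaged contrast exceeds 90%.

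**The case against.** A reader might infer that the plan commits to the interaction. It does not. Section 5.3 says effects will be tested with models that contain these terms. Such a model also gives visit-specific contrasts, and section 12 lists visits for which they could be reported. The power loss is therefore conditional on one reading. What stands is that nothing in the document rules that reading out or names another.

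A reader might also infer that the interaction misses any steady benefit under every coding. The figures do not support that: linear Time with baseline kept reaches 43–48% for 80% v 40%. Nor is the interaction always the weaker choice. For a widening gap, which fits the maintenance hypothesis, the linear interaction has 34–49%. It matches the averaged contrast in one case (49% each) and beats a post-treatment contrast (16–24%).

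A third inference would be that the sponsor intends to select among several tests. No section says so.

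Finally, sections 2.1 and 5.4 describe a preliminary trial that is not powered for all hypotheses. That answers a complaint about low power as such. It does not answer the absence of a defined primary test.

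**Conclusion.** The omission is certain: section 5.3 leaves the tested term, Time coding and baseline role open for the primary outcome, and no other section fills the gap. The consequence is conditional. If the interaction is the test, it does not address the synopsis objective. For a gap constant after baseline, its power is then:

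- categorical Time: about 3–11% with 0% baseline abstinence; 12–19% (4 df) or 19–27% (3 df) with 5%
- linear Time, baseline dropped: about 5–7%
- linear Time, baseline kept: about 5–20% for gaps of 25–30 points

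The averaged contrast was well ahead for every constant gap tried. For gaps that change over time the ranking is less one-sided.

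The percentages rest on assumed rates, correlation and loss, so they carry less confidence than the omission itself. The point concerns abstinence and should not be carried over to the continuous secondary outcomes. It should be fixed because the remedy is cheap and gives the one primary test an interpretable estimate.

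**What to change.** In section 5.3, for EDE-Q abstinence only:

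1. Do not model the pre-treatment visit as a response.
2. Treat Time as categorical over the post-baseline visits.
3. Name in advance one between-arm contrast as the primary test: the average over post-treatment, 3 and 6 months, or post-treatment alone if the sponsor wants to keep achieving abstinence separate from maintaining it.
4. Report the risk difference and odds ratio with 95% confidence intervals.
5. Keep the interaction and the 3- and 6-month contrasts as the maintenance analysis.

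A t-test on each patient's proportion of abstinent visits is an optional check. It rejected 5% under no effect with 17 per arm, but that run covered completers only. If it is used, the plan must say how randomised patients with no post-treatment visit enter it under the stated intent-to-treat or modified intent-to-treat approach.

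The adherence text in section 6 reports conduct in the past tense. If outcome data have already been examined, label the choice post hoc.

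The cost is SAP wording, with no new data or visits. The downside is that one contrast must be fixed in advance, and averaging dilutes a benefit that fades (27–32% power against 44–47% for post-treatment alone).

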5 STUDY EVALUATIONS AND MEASUREMENTS

5.1 Efficacy Evaluation

Preliminary efficacy (e.g. changes in binge-eating frequency, depression, anxiety, and relationship functioning) of UNITE will be assessed in comparison to the control group (CBT-E). Treatment gains will be assessed including observational and self-report measures. The primary outcome is abstinence from binge eating over the past 28 days measured with the EDE-Q. Secondary outcomes include EDE-Q binge frequency and global psychopathology, BES, Y-BOCS-BE, BDI-II, BAI, DERS, DERS-Partner, DAS, DAS-4, CPQ-SF, MSI-R (AFC and PSC), CSQ, and EDQOL.

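### The primary abstinence model could use each patient's pre-treatment binge frequency, which is already collected; leaving it out is valid but gives up some precision and leaves chance imbalance uncorrected

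*Combined protocol and SAP*

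**What the plan says.** Section 5.1 defines the endpoint: "The primary outcome is abstinence from binge eating over the past 28 days measured with the EDE-Q". It is binary and is measured in patients only.

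Section 5.3 gives the model: "For patient-only outcomes, differential treatment effects will be tested with multilevel mixed-effects models with fixed effects and two-way interactions for Time and Treatment", with a random effect for the patient. On distributions it says only that "Linear, logistic, and Poisson distribution functions will be used to model outcome variables", so a logistic link for abstinence is a reasonable reading. The one stated use of baseline data is descriptive: "Sociodemographics and baseline clinical characteristics will be summarized with descriptive statistics". No covariate is named for any outcome, and the plan does not say whether Pre is a level of Time.

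The baseline information exists. The questionnaire list in section 4.1 begins "ED100K, EDE-Q, BES, BE frequency, BDI-II", and Table 3 marks both EDE-Q and BE frequency at Pre for the patient. EDE-Q binge frequency is already a secondary outcome in section 5.1.

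The inclusion criteria in the Protocol Synopsis require "Current DSM-5 criteria for BED (one partner per couple"). Section 7 describes 1:1 stratified permuted-block randomisation without naming the strata.

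**The concern.** For a continuous or count outcome, treating Pre as one of the repeated measurements brings each patient's starting level into the analysis. For abstinence it does not. If every patient has current BED, nearly all are non-abstinent at Pre, and a response that hardly varies cannot separate a patient who binged rarely from one who binged often. The information lies in the count, and dichotomising discards it. The random patient effect is no substitute: it models correlation between visits of the same patient, while Treatment is compared between patients.

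The trial has about 19 patients per arm, and section 5.4 concedes that this does not give power for every hypothesis. If heavier bingeing at entry makes abstinence less likely, the planned model carries avoidable variance, and a chance difference between arms in starting severity passes straight into the primary comparison.

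**Working it through.** **Inputs from the documents.** 38 couples enrolled and 34 expected to complete (section 3.2), allocated 1:1 (section 7): 19 or 17 patients per arm.

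**Inputs assumed.** The documents give no abstinence rates, alpha or prognostic strength. Assumed: 35% v 65% abstinence at a single visit, two-sided 5%, and a within-arm correlation ρ between log baseline frequency and abstinence of 0, 0.30, 0.42 or 0.53. There is no power figure in the plan to reproduce; section 5.4 justifies 38 by a minimum number of groups for multilevel models.

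**1. Variance of the arm difference.** For one linear covariate and N patients in total, the adjusted/unadjusted ratio is about (1 − ρ²) × [1 + 1/(N − 4)]. With N = 38 the second factor is 1 + 1/34 = 1.03.

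| ρ | 1 − ρ² | × 1.03 |
|---|---|---|
| 0 | 1.00 | 1.03 |
| 0.30 | 0.91 | 0.94 |
| 0.42 | 0.824 | 0.85 |
| 0.53 | 0.719 | 0.74 |

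Simulated single-visit trials give about 0.94, 0.85 and 0.75, and 1.03 at zero. On the percentage-point scale, the unadjusted standard error at 19 per arm is √(2 × 0.35 × 0.65 / 19) = 0.155. Multiplying by the square roots of 0.94, 0.85 and 0.75 gives about 15.0, 14.3 and 13.4 points against 15.5.

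A separate check with Firth-penalised logistic regression and assumed rates of 40% v 70% gave variance ratios for the risk difference of 0.96, 0.91, 0.82 and 0.74 when the odds ratio for abstinence per SD of baseline frequency was 0.67, 0.5, 0.33 and 0.2.

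**2. Chance imbalance.** The standardised baseline difference between arms has SD √(2/19) = 0.324. The chance that it is at least 0.5 in either direction is 2 × [1 − Φ(0.5/0.324)] = 0.123. The shift in the unadjusted abstinence difference is about 0.5 × ρ × √(0.35 × 0.65) = 0.5 × ρ × 0.477: 7 points at ρ = 0.30, 10 at 0.42 and 13 at 0.53. In the Firth check the adjusted estimate shifted by less than 1 point.

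**3. Power.** The exact power of the unadjusted single-visit linear test is 0.450 at 17 per arm, 0.493 at 18 and 0.422 at 19. It falls between 18 and 19 because the outcome is discrete. Adjustment smooths this out, so even a covariate with ρ = 0 appears to gain about 2 points at 19 per arm and to lose about 5 at 18. At 17 per arm the gains are about 0, 4 and 9 points at ρ = 0.30, 0.42 and 0.53.

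**The case against.** The case for leaving the plan alone has real weight.

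- **The planned analysis is valid.** A reader might infer that it is biased or wrong. It is not: randomisation protects the unadjusted comparison, and in the simulations its type I error did not rise materially above 5%. This stands.
- **Large power gains are not supported.** A reader might take single-visit figures at 19 per arm, such as 42% to 49% at ρ = 0.30, as the benefit. They are partly an artefact of that sample size, as step 3 shows. The Firth check found only 39.5% to 40.7% at an odds ratio of 0.5 per SD, which corresponds to a similar correlation. Simulations of a random-intercept logistic model gave 68% to 74% at ρ = 0.31, but they used 250 replicates and tested one constant Treatment term, whereas section 5.3 specifies a Time by Treatment interaction. They show no gain for that test.
- **Prognostic strength is unknown.** Nothing in the documents says how well baseline frequency predicts abstinence. This stands, and it is why only a range is given.
- **Stratification may already help.** It would if binge severity were a factor, but section 7 names none and section 5.3 includes none in the model, so no protection can be assumed.
- **The trial is preliminary.** Section 2.1 frames it as feasibility, acceptability and preliminary effectiveness. That lowers the priority, but the synopsis still makes the comparison on abstinence the primary objective, and a small trial is where chance imbalance is most likely.

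**Conclusion.** The omission is real and specific to this endpoint: the count is collected, the model does not use it, and the binary value at Pre cannot replace it. That abstinence at Pre is about zero is an inference from the eligibility criteria, though a strong one.

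The consequence is modest and depends on the assumptions. The variance of the arm difference falls by about 6%, 15% or 25% at correlations of 0.30, 0.42 or 0.53, and rises by about 3% if baseline frequency predicts nothing. Protection against imbalance is the stronger argument: about a one-in-eight chance of a difference of 0.5 SD or more, with 0.5 SD worth 7 to 13 points on the primary estimate. These figures rest on 35% v 65% abstinence and a single visit, not on the full repeated-measures model. This is a cheap improvement to a valid analysis.

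**What to change.** In section 5.3, for EDE-Q abstinence, specify that the logistic mixed model is fitted to the post-baseline visits; that Time, Treatment and their interaction are kept; and that log(1 + EDE-Q 28-day binge episodes at Pre) enters as one pre-specified linear covariate with the same slope in both arms. Taking Pre out of the response also avoids a level with almost no events, which could cause separation in a logistic fit.

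A covariate changes the meaning of a logistic odds ratio, so report the standardised (marginal) difference in abstinence between arms, with the unadjusted proportions beside it.

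The cost is a sentence or two of wording, one extra parameter, and about 3% more variance if baseline frequency is not prognostic. No new data are needed. The covariate should be fixed before outcomes are examined by arm. Section 6 describes adherence monitoring in the past tense, so the trial may be well advanced; if outcomes by arm have already been examined, label the adjusted result a sensitivity analysis.

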---------------------------	---

Outcomes	
Primary outcome: Eating Disorder Examination-Questionnaire (EDE-Q) abstinence from binge eating (Fairburn & Beglin, 1994).
 
Secondary outcomes will include ED symptoms, depression and anxiety, couple-based measures, treatment satisfaction, and quality of life. ED symptoms will be measured with the Eating Disorder Examination-Questionnaire (EDE-Q; 28 items) binge frequency and global score (Fairburn & Beglin, 1994), the Binge Eating Scale (BES; 16 items) which measures binge eating severity (Gormally et al., 1982), and the Yale-Brown Obsessive Compulsive Scale Modified for Binge Eating (Y-BOCS-BE; 10 items) which measures the obsessiveness of binge-eating thoughts and compulsiveness of binge-eating behaviors (Deal et al., 2015). Beck Depression Inventory-II (BDI-II; 21 items) and Beck Anxiety Inventory (BAI; 21 items) will measure severity of current depressive and anxiety symptoms, respectively (Beck et al., 1988; Beck et al., 1996). Difficulties in Emotion Regulation Scale (DERS; 36-item) and the partner version (DERS-Partner; 8 items) will measure emotion regulation in oneself and one's partner, respectively (Gratz & Roemer, 2004). Dyadic Adjustment Scale (DAS; 32 items) and DAS-4 (4 items) will measure relationship satisfaction. Communication Patterns Questionnaire-Short Form (CPQ-SF; 12 items (Christensen & Heavey, 1990) modified for BED has two scores that will be calculated to assess how the couple communicates about the ED. These are a total score made up of the Self Demand/Partner Withdraw and Partner Demand/Self Withdraw subscales (6 items) and the Constructive Communication subscale (3 items). Marital Satisfaction Inventory (MSI-R; 32 items) affective communication (AFC) and problem-solving/communication (PSC) subscales will be used (Snyder, 1997). Treatment satisfaction will be measured with the Client Satisfaction Questionnaire (CSQ; 18 items). (Nguyen et al., 1983). Eating

-----------------	---

Disorders Quality of Life (EDQOL; 26 items) will measure the extent to which the ED affects quality of life (Engel, 2003). ED-related measures will be given to patients only and all other measures will be given to patients and partners.	

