12 PLANS FOR PUBLICATION

The primary outcome paper will include post-treatment, 3-month, and 6-month data on primary and secondary outcomes. Secondary papers will include coding of couple interactions and other secondary analysis results.

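### Section 5.3 makes no baseline adjustment for the continuous patient-only outcomes; the analysis is valid but may be less precise than the collected data allow

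*Combined protocol and SAP*

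**What the plan says.** The efficacy paragraph of section 5.3 is the fullest statement of the model. For patient-only outcomes, treatment effects are to be "tested with multilevel mixed-effects models with fixed effects and two-way interactions for Time and Treatment and a random effect for Patient". The synopsis gives the same structure in shorter form. Neither place lists the levels of Time, a baseline covariate, a constraint of equal arm means at Pre, or the visit at which an effect is read.

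The only explicit instruction about baseline values in section 5.3 is "Sociodemographics and baseline clinical characteristics will be summarized with descriptive statistics".

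The pre-treatment questionnaires in section 4.1 are "ED100K, EDE-Q, BES, BE frequency, BDI-II, BAI, DERS, DERS-Partner, DAS, CPQ-SF, R-BISF, CTS-2, MSI-R, EDQOL", and Y-BOCS-BE is among the interviews at the same visit. The synopsis restricts some of these: "ED-related measures will be given to patients only and all other measures will be given to patients and partners". Table 3 marks EDE-Q, BES, Y-BOCS-BE and EDQOL for the patient only, at Pre and at later visits.

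Two other places bear on whether Pre belongs to Time. Section 5.1 describes efficacy as "changes in binge-eating frequency, depression, anxiety, and relationship functioning". Section 12 states: "The primary outcome paper will include post-treatment, 3-month, and 6-month data on primary and secondary outcomes".

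On the primary outcome, section 5.1 says: "The primary outcome is abstinence from binge eating over the past 28 days measured with the EDE-Q". The synopsis entry criterion for the patient is "Current DSM-5 criteria for BED (one partner per couple".

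**The concern.** In a randomised comparison of a continuous outcome that is also measured at baseline, conditioning on the baseline value usually narrows the confidence interval at almost no cost. Section 5.3 does not do this. If Pre is a level of a categorical Time factor with free arm means, the Time by Treatment contrast at a later visit is a difference in mean change. If Pre is left out of Time, the contrast is a difference in raw follow-up means. Neither makes the best use of the Pre value, except in special cases.

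The stake is interval width in a small trial. Section 5.4 concedes that 38 couples do not give power for every hypothesis, so precision available from data already collected is worth having. Four of the 14 secondary measures listed in section 5.1 are affected: EDE-Q global, BES, Y-BOCS-BE and EDQOL.

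The primary outcome raises a separate, smaller matter. If almost no patient is abstinent at Pre, a contrast referenced to Pre is unusable on the logit scale, and section 5.3 does not say that another contrast is the test.

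**Working it through.** **The plan's own figure.** Section 5.4 justifies 38 couples by the number of groups needed for unbiased standard errors. It gives no power, standard error or detectable difference, so there is no precision figure to reproduce. Section 3.2 aims for 34 completing couples, which at 1:1 allocation (section 7) is n = 17 patients per arm.

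**Assumptions.** Complete data; one baseline and one follow-up value per patient; follow-up SD = 1; baseline SD = k; baseline-to-follow-up correlation r = 0.3, 0.5, 0.7. Neither r nor k is in the documents. Because only two visits enter, the result applies to Y-BOCS-BE as well, at visits where it is measured (it has no 3-month assessment).

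**Variance of the between-arm effect.**

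- Change from Pre: (2/n)(1 + k² − 2rk)
- Follow-up means without covariate: 2/n
- Baseline-adjusted: (2/n)(1 − r²) × f, where f = 1 + 1/(2n − 4) = 1 + 1/30 = 1.033 allows for estimating the slope

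**Equal SDs (k = 1), adjusted against change.** The ratio is f(1 − r²)/[2(1 − r)].

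- r = 0.3: 1.033 × 0.91/1.40 = 0.67
- r = 0.5: 1.033 × 0.75/1.00 = 0.78
- r = 0.7: 1.033 × 0.51/0.60 = 0.88

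**Unequal SDs, adjusted against change.** The ratio is f(1 − r²)/(1 + k² − 2rk).

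| Baseline SD / follow-up SD | r = 0.3 | r = 0.5 | r = 0.7 |
|---|---|---|---|
| 0.7 | 1.033 × 0.91/1.07 = 0.88 | 1.033 × 0.75/0.79 = 0.98 | 1.033 × 0.51/0.51 = 1.03 |
| 1.0 | 0.67 | 0.78 | 0.88 |
| 1.3 | 1.033 × 0.91/1.91 = 0.49 | 1.033 × 0.75/1.39 = 0.56 | 1.033 × 0.51/0.87 = 0.61 |

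The 1.03 cell has a simple explanation. The slope of follow-up on baseline is r/k = 0.7/0.7 = 1, so the change score is already the best adjustment and estimating the slope only costs the 3%.

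**Adjusted against follow-up means (Pre outside Time).** The ratio is f(1 − r²) = 0.94, 0.78, 0.53, whatever k is. It falls below 1 only when r exceeds √(1 − 1/1.033) ≈ 0.18.

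**Simulation check.** With k = 1 and 40,000 trials at each r, the ratios were 0.673, 0.781 and 0.875 against change, and 0.941, 0.775 and 0.533 against follow-up means. Type I error was 4.9% to 5.1% for all three analyses.

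**Abstinence.** A categorical contrast referenced to Pre is [logit p(UNITE, visit) − logit p(UNITE, Pre)] minus the same quantity for CBT-E. If both Pre proportions are 0, both Pre logits are minus infinity and the contrast has no finite estimate. The between-arm log odds ratio at a post-baseline visit does not use the Pre proportions and can be estimated.

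**The case against.** The strongest reply is that nothing here is an error. Time, Treatment, their interaction and a random patient effect form a standard model, all the analyses compared hold their type I error, and the trial presents itself as a test of feasibility, acceptability and preliminary effectiveness. All of that stands, and it limits the point to efficiency.

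A second reply is that the size of the gain is not known. This also stands. A reader might infer from the equal-SD row that adjustment is worth a fixed number of couples, for example 34/0.775 − 34 ≈ 10 at r = 0.5. The documents do not support a fixed number. At the same r, an SD ratio of 0.7 makes it less than one couple (34/0.981 − 34 ≈ 0.7). Requiring current BED at entry could narrow the baseline spread, so a ratio below 1 is not far-fetched.

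A reader might also take the ratio of 0.53 at r = 0.7 as the headline. It requires Pre to lie outside Time. The only support for that is section 12, a publication plan that also leaves out the mid-treatment visit and specifies no model. The talk of changes in section 5.1 and the visit columns of Table 3 make Pre as a level of Time the likelier reading. For the same reason, the descriptive summary of baseline data in section 5.3 should not be read as proof that Pre values are kept out of the model.

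Finally, a reader might conclude that the primary analysis cannot be estimated, or that a baseline covariate would sharpen it. Neither follows. Zero abstinence at Pre is an inference from the entry criterion, other contrasts in the same model remain estimable, and in a logistic model covariate adjustment changes the conditional odds ratio and need not reduce its standard error.

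**Conclusion.** The point holds as an avoidable loss of precision for EDE-Q global, BES, Y-BOCS-BE and EDQOL. It is not a bias or validity fault. On the likelier reading, with 17 complete patients per arm and equal SDs, adjustment brings the variance to about 0.67 to 0.88 of the planned contrast over r = 0.3 to 0.7. Over SD ratios of 0.7 to 1.3 the range widens to 0.49 to 1.03, so the benefit runs from large to a loss of about 3%. If Pre is outside Time, the range is 0.53 to 0.94. Every figure rests on assumed correlations and SDs.

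The figures do not extend to EDE-Q binge frequency (a count), CSQ (post-treatment only), DAS-4, or outcomes given to both partners. For abstinence the conclusion is only that a contrast referenced to Pre should not be the test.

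**What to change.** In section 5.3, for the four continuous patient-only outcomes, take the post-baseline visits as the response, enter the Pre value as a covariate, and read the UNITE minus CBT-E effect at a named visit. Constraining the arm means to be equal at Pre in the longitudinal model is an acceptable alternative. In that case let the variance at Pre differ from later visits, because a random intercept alone implies equal SDs and would fix the adjustment accordingly.

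For abstinence, state that the test is the between-arm contrast at a named post-baseline visit, not a Time by Treatment contrast referenced to Pre. A baseline covariate there is optional; with about 17 patients per arm it may make the logistic model less stable.

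The change needs no new data. It costs one degree of freedom, about 3% in variance when adjustment gives no gain. Section 6 already describes trial conduct in the past tense, and the documents do not say whether outcomes had been examined when the text was written. The change should therefore be dated, and labelled post hoc if they had.
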